5.6 Contingency Plans During the COVID-19 Pandemic

- Safety oversight: In case a patient cannot return to the study site for the scheduled visit, the site staff will contact the patient remotely for safety follow up, for example, via telephone or video conferencing.
- Central Laboratory: In the case there are courier issues that will prevent the protocol-required laboratory specimens to be sent to the study core laboratory, the site should have the safety laboratory specimens ([Table 2: Hematology, Chemistry, and Urinalysis](#)) sent to their local laboratory for analysis and review by the study physician.
- Investigational Product Dosing: In cases when dosing cannot be performed during the protocol-designated windows, the Investigator should discuss each case with the Sponsor to determine whether it is a missed visit or whether the dosing can be performed outside protocol windows (as a protocol deviation). A minimum of 2 weeks must be maintained between consecutive doses. Patients who miss more than 2 doses of the study drug (whether consecutive or not) will be discontinued from the study and will undergo assessments as outlined in [Section 5.5](#) (Premature Discontinuation).

6 ASSESSMENTS

Every effort should be made to ensure that the protocol required tests and procedures are completed as described. However, it is anticipated that from time to time there may be circumstances, outside of the control of the Investigator, which may make it unfeasible to perform the test. In these cases, the Investigator will take all steps necessary to ensure the safety and wellbeing of the patient. When a protocol required test cannot be performed the Investigator will document the reason for this and any corrective and preventive actions which he/she has taken to ensure that normal processes are adhered to as soon as possible. All protocol violations are entered directly into the eCRFs.

6.1 Medical History, Demographic and Other Baseline Information

The medical history comprises:

- General medical history
- Documentation of SLE diagnosis
- Historical medication therapy for SLE

The following demographic information will be recorded:

- Age
- Ethnic origin (Hispanic/Latino or not Hispanic/not Latino)
- Race (White, American Indian/Alaska Native, Asian, Native Hawaiian or other Pacific Islander, Black/African American)
- Height (without shoes, in cm)
- Body weight, without shoes (kg)
- BMI [kg/m²]

Other baseline characteristics will be recorded as follows:

- Concomitant medication documentation (see [Section 4.6](#))
- Status of child bearing potential and contraception

6.2 Safety Assessments

6.2.1 Laboratory Assessments

Laboratory tests will be performed at times defined in the Schedule of Assessments ([Table 1](#) and [Table 4](#)). Patient eligibility will be determined based on these tests at screening. Unscheduled clinical labs may be obtained at any time during the study to assess any perceived safety concerns.

A central laboratory will be used (with the exception of urine pregnancy tests) to ensure accuracy and consistency in test results. Laboratory/analyte results that could unblind the study (i.e., biomarker results) will not be reported to investigative sites. Urinalysis

will be performed on midstream, clean catch specimens. Some biomarkers listed above will not be drawn at some sites due to geographical logistical challenges. See the laboratory manual for details.

Endpoint analyses will be based on changes from baseline assessments at Days 120 and 210.

Table 2. Laboratory Tests

Hematology	Chemistry	Urinalysis	Other Safety Tests
Hemoglobin	BUN	pH	Spot urine for protein/creatinine ratio
Hematocrit	Creatinine	Glucose (qual)	FSH ^b
RBC count	Glucose (fasting)	Protein (qual)	Urine pregnancy test ^c
RDW	Calcium	Blood (qual)	QuantiFERON [®] -TB Gold In-Tube test (QFT-G) ^d
MCV	Sodium	Ketones	Serology ^d (Hepatitis B and C; HIV-1/2 combination)
MCH	Potassium	Nitrites	Stool sample ^e
MCHC	Chloride	Leukocyte esterase	Serum pregnancy test
Platelet count	Total CO ₂ (bicarbonate)	Urobilinogen	
WBC count	AST, ALT	Urine bilirubin	
CD4+ count	Total bilirubin	Microscopy ^a	
Total neutrophils (Abs)	Alkaline phosphatase		
Eosinophils (Abs)	Creatine kinase		
Monocytes (Abs)	Uric acid		
Basophils (Abs)	Albumin		
Lymphocytes (Abs)	Total cholesterol (fasting)		
	LDL-C (fasting)		
	HDL-C (fasting)		
	Triglycerides (fasting)		
	Total protein		
	PT/INR		
	Additional Tests^f (potential Hy's Law)		Immunogenicity, PD and other Biomarker Tests
	AST, ALT (repeat)		ADA
	Total bilirubin (repeat)		nAb ^g
	Albumin (repeat)		pSTAT3 (predose [trough] samples only in phase 1b)
	Alkaline phosphatase (repeat)		Total IgG & IgM
	Direct bilirubin		Plasma CCI [REDACTED]
	Indirect bilirubin		Plasma CCI [REDACTED] & CCI [REDACTED]
	GGT		Whole blood for leukocyte immunophenotype (for MAD patients only)
	Prothrombin time/international normalized ratio (repeat)		CCI [REDACTED]
	Creatine kinase (repeat)		CCI [REDACTED]
			[REDACTED]
			CRP
			Direct Coomb's test ^h

Table 2. Laboratory Tests

Hematology	Chemistry	Urinalysis	Other Safety Tests
Abbreviations: Abs = absolute; ADA = anti-drug antibody; ALT = alanine aminotransferase; CCI [REDACTED]; CCI [REDACTED]; AST = aspartate aminotransferase; BUN = blood urea nitrogen; C = complement; CD4+ = cluster of differentiation 4; CRP = C-reactive protein; dsDNA = double-stranded deoxyribonucleic acid;; FSH = follicle stimulating hormone; GGT = gamma-glutamyltransferase; HDL-C = high-density lipoprotein cholesterol; HIV = human immunodeficiency virus; IgG = immunoglobulin G; IgM = immunoglobulin M; INR = international normalized ration; IL-21 = interleukin 21; LDL-C = low-density lipoprotein cholesterol; MAD = multiple ascending doses; MCH = mean corpuscular hemoglobin; MCHC = mean corpuscular hemoglobin concentration; MCV = Mean corpuscular volume; nAb = neutralizing antibody; pSTAT3 = phosphorylated signal transducer and activator of transcription 3; PT = prothrombin time; qual = qualitative; RBC = red blood cell; RDW = RBC distribution width; SAE = serious adverse event; SC = subcutaneous; CCI [REDACTED]; TB = tuberculosis.			
a On all urine samples			
b At screening only, in women who are amenorrheic for at least 12 consecutive months and under 55 years old			
c For WOCBP			
d Screening only			
e At screening, and if a patient develops diarrhea during the study a stool sample must be provided to test for ova, parasites, and cryptosporidium			
f Additional testing for potential Hy's Law cases only (See Section 6.2.2.6.3)			
g If patient is positive for ADA			
h If clinically indicated for hemolytic anemia			

6.2.1.1 Pregnancy testing

For WOCBP, a serum pregnancy test will be performed at screening. Following a negative serum pregnancy result at screening, appropriate contraception must be commenced or continued and a further negative urine pregnancy test results will then be required at the baseline visit before the patient may receive the investigational product. Urine pregnancy tests will also be routinely repeated at study drug administration visits prior to study drug administration, at the last follow up visit day (Day 270) and additionally whenever 1 menstrual cycle is missed or when potential pregnancy is otherwise suspected. In the case of a positive pregnancy test or confirmed pregnancy, the patient will be discontinued from study drug, an EOT visit should be performed (Day 180), and a last follow-up visit 90 days after last dose should be scheduled (Day 270). Safety follow-up visit procedures (see [Section 5.4](#)) are specified in the Schedule of Assessments (see [Table 1](#) and [Table 4](#)).

See [Section 6.2.2.7.1](#) for information on reporting of pregnancies as AEs/SAEs during the study.

6.2.1.2 Tuberculosis Screening

During the screening period, it must be determined and documented that a patient does not have evidence of active or latent or inadequately treated TB per the exclusion criteria ([Section 4.5](#)). The results of TB screening, which includes the QuantiFERON®-TB Gold In-Tube (QFT-G) test and a chest x-ray, conducted in the

3 months prior to screening or during the screening period must be documented in study records prior to randomization (Day 0).

6.2.1.2.1 Mycobacterium Tuberculosis Testing Using QuantiFERON Test⁴⁰

QuantiFERON-TB Gold In-Tube (QFT-G) is an *in vitro* diagnostic test using a peptide cocktail simulating ESAT-6, CFP-10, and TB 7.7 proteins to stimulate cells in heparinized whole blood. Detection of INF γ performed by enzyme-linked immunosorbent assay (ELISA) is used to identify *in vitro* responses to these peptide antigens that are associated with Mycobacterium tuberculosis infection. QFT-G is an indirect test for M. tuberculosis infection (including disease) and is intended for use in conjunction with risk assessment, radiography and other medical and diagnostic evaluations.

Test results will be reported as positive, negative, or indeterminate. A negative QFT-G test result is required to meet the inclusion criterion. In the case of an indeterminate result, repeat tests should be permitted for the purpose of determining eligibility of patients to enroll in this study. If a repeat test is indeterminate again, the patient is a screen failure. The procedure for using this test and interpreting the results will be described fully in the laboratory manual, which will be provided to Investigators.

6.2.2 Adverse Events

6.2.2.1 Definitions

An AE is defined as any untoward medical occurrence experienced by a study patient, whether or not considered drug related by the principal Investigator.

AEs are unfavorable changes in a general condition, subjective or objective signs or symptoms, worsening of pre-existing concomitant disease, and clinically significant abnormality in laboratory parameters observed in a patient in the course of a clinical study.

Non-serious SLE manifestations or abnormal laboratory results related to SLE disease activity would not be recorded as AEs unless they meet the definition for SAEs ([Section 6.2.2.5](#)).

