1.2.5 Potential Risks

Potential risks based on the mechanism of action of BOS161721 include infections, risks associated with the administration of any foreign protein or biologic agent, including injection site reaction, anaphylaxis, serious allergic reaction, and development of ADAs. ADAs could result in immune complex disease (with manifestations such as arthralgias, serum-sickness, and vasculitis), or altered BOS161721 levels or activity. Further details can be found in the current Investigator's Brochure (IB) for BOS161721, which contains comprehensive toxicology, preclinical and clinical information on BOS161721.

Two investigational drug products are considered to be in the same pharmacological class as BOS161721 based on interruption of signaling through the IL-21 signaling pathway. No potential risk generalizable across the class has been observed with these investigational products. Based on the clinical phase 1 SAD study (BOS161721-01), AEs reported as related to the study drug, particularly infections (flu-like symptoms, etc.), were expected for the compound, and there were no clinically relevant changes in laboratory and ECG results or vital signs.

The majority of IgG elimination occurs via intracellular catabolism, following fluid-phase or receptor-mediated endocytosis. This type of endocytosis and elimination is a form of target-mediated disposition where the interaction of the drug and its pharmacological target (e.g., a target receptor) serves as a significant contributor to the kinetics of antibody distribution and elimination. Renal elimination, which is a primary pathway of clearance of small-molecule drugs, is relatively unimportant for IgG, as its large size prevents efficient filtration through the glomerulus. Secretion into the bile is an important pathway of elimination of IgA antibodies, but this route is not a significant contributor to the elimination of IgG antibodies. Thus, risk to renal and hepatic systems due to metabolism of BOS161721 is low.³³

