1.2.5.3 Immune Complex Disease

The potential risk of immune complex disease for BOS161721 is theoretical, based on the known risks associated with mAbs. The administration of a mAb can result in the formation of ADAs. Administration of the mAb in the presence of ADA may result in the formation of circulating antibody-antigen complexes potentially resulting in altered BOS161721 levels or activity or deposition of the complexes in microvasculature. Complement is frequently involved in the latter setting, and the breakdown products of complement attract polymorphonuclear leukocytes to the site of deposition where they can provoke local tissue damage through specific or nonspecific release of enzymes. Two of the more common end-organ targets are the blood vessels (vasculitis) and kidney (nephritis). These clinical manifestations represent immune complex disease or Type III hypersensitivity. Although BOS161721 is a humanized mAb, ADAs may develop; however, the likelihood of occurrence of immune complex disease with BOS161721 is low. The findings of immune complex disease are typically reversible when mAb administration stops and the antibody-antigen complexes are cleared from the body.

Based on the phase 1 SAD study (BOS161721-01), immune complex disease in subjects who received BOS161721 was not observed.

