4.4 Inclusion Criteria

Patients who meet the following criteria will be considered eligible to participate in this clinical study:

1. Men and women, ages 18 to 70 years, inclusive.

2. Patients must be mentally capable of giving consent and there must be evidence of a personally signed and dated informed consent document indicating that the patient has been informed of all pertinent aspects of the study.
3. Patients must have SLE as defined by meeting 4 of the Systemic Lupus International Collaborating Clinics (SLICC) classification criteria for SLE (with at least 1 clinical and 1 immunologic criterion or Lupus nephritis as the sole clinical criterion in the presence of ANA or anti-dsDNA antibodies), either sequentially or simultaneously.
4. At screening, patients must have at least 1 of the following:
 - a. Elevated ANA \geq 1:80 via immunofluorescent assay at the central laboratory
 - b. Positive anti-dsDNA or anti-Smith (Sm) above the normal level as determined by the central laboratory
5. At screening, the total SLEDAI-2K score must be \geq 8, including points from at least 1 of the following clinical components:
 - a. Arthritis, rash, myositis, mucosal ulcers, pleurisy, pericarditis, and vasculitis
Note: Points from lupus headache and organic brain syndrome will also be excluded from qualifying total and clinical SLEDAI-2K scores at screening and Day 0.
6. A clinical SLEDAI-2K score of \geq 6 at screening at Day 0. Clinical SLEDAI-2K score is defined as follows:
 - a. Contains points from arthritis, rash, myositis, mucosal ulcers, pleurisy, pericarditis, or vasculitis
 - b. Excludes parameters which require central laboratory results: hematuria, pyuria, urinary casts, proteinuria, positive anti-dsDNA, decreased complement, thrombocytopenia, and leukopenia
Note: Points from lupus headache and organic brain syndrome will also be excluded from qualifying total and clinical SLEDAI-2K scores at screening and Day 0.
7. Patients must have at least 1 qualifying A or 2Bs from the following manifestations of SLE, as defined by the BILAG criteria as modified for use in this study, which must be confirmed by the central data reviewer:
 - a. BILAG A or B score in the mucocutaneous body system. If a BILAG B score is due to BILAG number 6, mild skin eruption, the CLASI activity score including erythema and scale/hypertrophy must be \geq 3 excluding points from mucosal ulcers and alopecia.

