6.2.2.6 Adverse Events of Special Interest

AEs of special interest in this study include the following:

1. Anaphylaxis and serious allergic reactions
2. Grades 2 to 5 injection site reaction, including erythema, pain, and induration (see [Appendix 6](#))
3. Drug Induced Liver Injury (DILI) assessed following Hy's Law
4. Malignancy (not including basal cell carcinoma or squamous cell carcinoma of skin)
5. Opportunistic infections such as disseminated histoplasmosis, cryptococcosis, disseminated herpes simplex, disseminated tuberculosis, *Aspergillus* sp., *Candida albicans*, *Coccidioides immitis*, *Cryptococcus neoformans*, *Cytomegalovirus*, *Histoplasma capsulatum*, *Isospora belli*, and *Polyomavirus JC polyomavirus*

6. Cryptosporidiasis

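### Non-serious immune complex disease that looks like lupus can be left out of the adverse event data, and this named risk has no special-interest entry to prevent that

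*Protocol*

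**What the plan says.** Section 1.2.5 of the protocol states that "ADAs could result in immune complex disease (with manifestations such as arthralgias, serum-sickness, and vasculitis), or altered BOS161721 levels or activity". Section 1.2.5.3 adds that complement is often involved, that blood vessels and kidney are among the more common target organs, and that the clinical picture is a Type III hypersensitivity. It also puts the risk in proportion: "The potential risk of immune complex disease for BOS161721 is theoretical, based on the known risks associated with mAbs". It calls the likelihood low and the findings typically reversible once the antibody is stopped, and it reports no case in the single-dose study.

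Section 6.2.2.1 defines AEs broadly and then makes an exemption: "Non-serious SLE manifestations or abnormal laboratory results related to SLE disease activity would not be recorded as AEs", unless they meet the SAE definition.

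The AESI list in Section 6.2.2.6 has six items. It opens with "Anaphylaxis and serious allergic reactions" and continues with Grade 2 to 5 injection site reactions, drug-induced liver injury, malignancy, opportunistic infections and cryptosporidiosis. Immune complex disease is not on it.

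**The concern.** The exemption in Section 6.2.2.1 is a sensible rule for lupus trials, because it keeps ordinary disease activity from swamping the AE tables. It becomes a problem when a risk attributed to the drug looks like the disease. A patient who develops mild vasculitis, joint pain or proteinuria some weeks after a dose may have a flare or may have ADA-mediated immune complex disease. The protocol gives no rule for telling the two apart. If the investigator settles on lupus and the event is not serious, no AE is recorded.

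At stake is the AE incidence of a risk that the protocol itself names, in the arm where it can occur. A SAP can add analyses by arm or by ADA status, but it cannot recover AEs that were never recorded, so the point belongs in the protocol. Section 1.2.5.3 describes the findings as typically reversible, so non-serious cases are where recognition is most useful, and they are the cases the exemption covers.

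**Working it through.** The plan gives no figure to reproduce on this point. The check sets the sections side by side.

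**1. Do the named signs overlap with lupus as the protocol defines it?**

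| Named manifestation (1.2.5, 1.2.5.3) | Treated as a lupus feature in Section 4.4? |
|---|---|
| Arthralgia | Overlaps: arthritis is among the qualifying SLEDAI-2K components, "Arthritis, rash, myositis, mucosal ulcers, pleurisy, pericarditis, and vasculitis" |
| Vasculitis | Yes: same list |
| Nephritis | Yes: "Lupus nephritis as the sole clinical criterion in the presence of ANA or anti-dsDNA antibodies" counts for classification; proteinuria and urinary casts are SLEDAI-2K laboratory items |
| Serum sickness | No: not given as a lupus feature anywhere in the protocol |

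Three of four overlap. Decreased complement, the laboratory correlate in Section 1.2.5.3, is also a SLEDAI-2K item.

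**2. Which named risks have an AESI entry?**

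| Risk section | AESI entry in 6.2.2.6 |
|---|---|
| 1.2.5.1 Anaphylaxis and serious allergic reactions | Yes |
| 1.2.5.2 Injection site reactions | Yes (Grades 2 to 5) |
| 1.2.5.3 Immune complex disease | None |
| 1.2.5.4 Infections | Yes (opportunistic infections; cryptosporidiosis) |
| 1.2.5.5 Malignancy | Yes |
| 1.2.5.6 Hepatic function abnormality | Yes (drug-induced liver injury) |

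Five of six have an entry. The protocol does not explain the omission.

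**3. What exactly does the exemption remove?** An event must be both non-serious and judged a lupus manifestation or a lupus-related laboratory abnormality. A serious event is recorded as an SAE. An event not judged to be lupus is an AE under the broad definition, and Section 6.2.2.2 allows individual symptoms to be reported when no diagnosis is established.

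**4. Do neighbouring rules close the gap?** They do not, and two of them widen it. Table 3 in Section 6.2.2.4 allows a causality of related only when concurrent disease cannot explain the event, which is hard to meet for these signs in a lupus patient. Section 6.2.8 and the Table 1 footnote on ADA limit assays after Day 90 to patients who were positive on Day 90, while dosing continues on Days 120, 150 and 180. An ADA response that first appears after Day 90 is therefore not seen.

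**5. What is captured regardless of AE recording?** Section 2.2 makes clinical laboratory changes, physical examination changes and ADAs safety endpoints of the phase 2 part. Table 2 lists the spot urine protein/creatinine ratio as a safety test. Table 1 schedules it, with urinalysis, at screening, Day 0, the monthly visits and follow-up to Day 270. Under Section 6.2.5 the targeted examination covers lupus-related issues. ADA is assayed in all patients through Day 90. BILAG flares are compared between the randomized arms.

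**6. Exposure.** With 2:1 randomization of about 110 patients (Section 3.1.2.2), 110 × 2/3 ≈ 73 receive active drug, for up to 7 doses each. No event frequency is given, so no count of missed cases follows.

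**The case against.** The strongest reply is that this is a choice of AESI scope for a risk the protocol calls theoretical and unlikely, and that other data cover it. Much of this stands. Renal signs in particular reach the safety data through urine and chemistry results whether or not an AE is written down. The disease-activity instruments are also reviewed centrally by the medical monitor and sponsor (Section 3.1).

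A reader might infer that every listed sign is a lupus sign, so that the trial cannot detect immune complex disease. The documents do not support this. Serum sickness is not a lupus item here and is an ordinary recordable AE. Serious cases are SAEs. Severe cases arguably fall under the hypersensitivity wording of Section 6.2.2.6.1. It would also go too far to say that sites will always choose lupus, which is a prediction about investigators' behaviour. Nor can one say that the DMC would see nothing until a case is serious: the DMC reviews unblinded data (Section 3.2), and its tables are set in a charter that is not shown.

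The reply does not remove the gap. The single-dose study enrolled healthy subjects, in whom vasculitis or nephritis could not be mistaken for lupus, so the absence of cases there says little about recognition here. The BILAG flare endpoint needs at least one A or more than one B score, so a single milder sign may not count. Net disease-activity scores could also mask such events if the drug lowers activity overall. The safety review for dose selection in Section 3.1.2.1 is described as focused on AEs, SAEs and AESIs, which are the categories from which non-serious lupus-like cases may be missing.

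**Conclusion.** The point holds as a limited under-recording problem. Non-serious immune complex disease presenting as arthralgia, vasculitis or nephritis and attributed to lupus is not recorded as an AE, and no AESI entry directs attention to it. Its extent is three of four named manifestations, and one of six named clinical risks without an AESI entry. Its effect on AE counts cannot be quantified, because it depends on an unstated event frequency and on how often investigators attribute such events to lupus.

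The conclusion assumes that sites follow Section 6.2.2.1 as written and that no other study document, such as the eCRF completion guidelines or the DMC charter, adds an exception. It does not say that the risk is likely, or that the trial would miss it altogether. This is a cheap improvement, not a flaw that undermines the trial.

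**What to change.** 1. In Section 6.2.2.6, add *suspected immune complex disease / Type III hypersensitivity (including serum sickness)* to the AESI list.
2. In Section 6.2.2.1, add a narrow exception: vasculitis that is new since baseline, new signs of nephritis, or a serum-sickness-like picture, arising after the first dose, is recorded as an ordinary AE whatever its presumed cause. AESI reporting applies only when immune complex disease is actually suspected. Limiting the exception to new-onset findings matters, because patients may enter with active arthritis or vasculitis, and AESI status triggers reporting immediately or within 24 hours (Section 6.2.2.7.3).
3. Tabulate these AEs by arm, separately from other AEs, beside whatever scheduled ADA, complement and urine protein results exist for the patient.

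The cost is protocol and eCRF-guideline wording, with no new visit. Some lupus flares in both arms will appear as AEs, and a few more events will need 24-hour reporting. ADA support will be incomplete: after Day 90, phase 2 samples are drawn only on Days 180 and 270 and are not assayed in patients negative on Day 90. Later events in those patients will have no ADA result unless the samples already collected are assayed, and a Day 120 or Day 150 event would have no contemporaneous one even then.
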